2.3 Endpoints

2.3.1 **Primary Endpoint**

 The primary efficacy endpoint of the study is clinical ruxolitinib response of quantitative ΔTumor size measured as a proportional percent (range -100% to +100%) from baseline to day 14-21.

Phase 2 - Ruxolitinib Page 23 of 67

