- 11. Concomitant Medications, any of the following should be considered for exclusion: Strong CYP3A4 inhibitors: (Patients must discontinue drug 7 days prior to starting ruxolitinib), including but not limited to boceprevir, clarithromycin, conivaptam, indinavir, itraconazole, ketoconazole, lopinavir, mibefradil, nefazodone, nelfinavir, posaconazole, ritonavir, saquinavir, telaprevir, telithromycin, or voriconazole. In addition, patients will be instructed to avoid grapefruit or grapefruit juice, starfruit, or Seville oranges.
- 12. Prisoners or participants who are compulsorily detained (involuntarily incarcerated) for treatment of either a psychiatric or physical (e.g., infectious) illness.

3.4 **Duration of Therapy**

In the absence of treatment delays due to adverse events, treatment will only be during the preoperative window of 14-21 days or up to 28 days for delays in planned surgery or until:

- Progressive disease at any time
- Any clinical adverse event, laboratory abnormality or intercurrent illness which, in the
 opinion of the Investigator, indicates that continued treatment with study therapy is not in
 the best interest of the participant
- Excessive toxicity
- Withdrawal of informed consent (participant's decision to withdraw for any reason)
- Pregnancy
 - All women of childbearing potential should be instructed to contact the Investigator immediately if they suspect they might be pregnant (e.g., missed or late menstrual period) at any time during study participation.
 - The Investigator must immediately notify Incyte in the event of a confirmed pregnancy in a patient participating in the study.
 - Study Closure or termination
 - Noncompliance

3.5 **Duration of Follow Up**

Patients will be followed for up to 12 weeks post-operation, as deemed clinically necessary or removal from study, or until death, whichever occurs first. Patients removed from study for unacceptable treatment related adverse event(s) will be followed until resolution or stabilization of all treatment related adverse events to Grade 2 or lower.

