3.5.1 Procedures for discontinuation

Participants who discontinue should, if possible, be seen and assessed by an investigator(s). The reason for withdrawal and the date of withdrawal must be documented. If possible, any diary cards and investigational products should be returned by the participant as soon as possible after study discontinuation. If patient had screening tissue samples obtained, has taken at least 14 days of drug, and has undergone response assessment, they are evaluable.

If the reason for withdrawal from the trial is the death of the participant, the two options for categorizing withdrawal are either disease recurrence or an adverse event (AE; more than one

Phase 2 - Ruxolitinib Page 27 of 67

AE may be documented as a reason for withdrawal). Only one event will be captured as the cause of death.

Note: death is an outcome and not an AE. All deaths that occur within the trial period or within 30 days after administration of the last dose of trial drug must be reported to Incyte primarily for the purposes of serious adverse event (SAE) reporting; however, deaths due unequivocally to progression are not SAEs.

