4.4 Packaging and Labeling of Study Drugs

Drugs will be packaged and labeled per UCSF institutional standards, adhering to applicable local and federal laws.

5 Treatment Plan

5.1 **Dosage and Administration**

Treatment will be administered on an outpatient basis.

Table 5.1 Regimen Description

Study Drug	Dose	Route	Schedule	Cycle Length
Ruxolitinib	20mg or 15mg dependent on baseline	РО	BID	Pre-operative window (14-21 days) or up to 28 days for delayed
	platelet count			surgery

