6.3.2 Treatment Period

Days 1-28; **NOTE** ruxolitinib treatment is planned for 14-21 days, however may be administered up to 28 days if required for logistical/scheduling purposes.

6.3.2.1 **Day 1**

Ruxolitinib will be administered at the FDA-approved dose in myelofibrosis, as determined by baseline platelet count: 1) Patients with a platelet count ≥ 200,000 will take 20 mg bid (four 5mg tablets in the morning and four 5mg tablets in the evening); 2) participants with a platelet count ≥ 150,000 and < 200,000 will take 15 mg bid (three 5 mg tablets in the morning and three 5 mg tablets in the evening). Ruxolitinib will be discontinued on the day of surgical resection (following the morning dose). If surgery is delayed, the study drug may be continued until surgery, for a

Phase 2 - Ruxolitinib Page 38 of 67

Protocol CC# 16201

maximum of 28 days. Fourteen days is the minimum required treatment for a patient to be considered evaluable. The interval between the last dose of ruxolitinib and surgery will be 2-24 hours.

Ruxolitinib will be dispensed as 5mg tablets. Participants with a platelet count \geq 200,000 will take 20 mg bid (four 5mg tablets in the morning and four 5mg tablets in the evening). Participants with a platelet count \geq 150,000 and < 200,000 will take 15 mg bid (three 5 mg tablets in the morning and three 5 mg tablets in the evening).

Participants will be asked to indicate on a drug diary (see Appendix 4) when doses of study drug are taken in order to monitor for compliance. Participants may also use the drug diary for notations on side effects and other treatment related events.

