6.3.2.2 Day 9-28 (inclusive of day of surgery)

Post-treatment, pre-surgical

NOTE: all efforts should be made to schedule these evaluations on the day prior to or the day of surgery, however a 5 day window is provided for logistical purposes.

- History and Physical Examination (Post-treatment, Pre-operative): Participants will be evaluated by history and physical examination by the treating physician within 5 days prior to planned surgery (including vital signs, weight, performance status). This visit will also include toxicity and compliance assessment. Compliance as evidenced by pill count and patient drug diary will be assessed. For logistical convenience, this visit may be scheduled in conjunction with blood collection and imaging as specified below. NOTE: Participants will continue to take ruxolitinib until the morning of planned surgery. If surgery is delayed, participants will continue to take ruxolitinib and this pre-operative history and physical examination does not need to be repeated.
- Blood Collection (Clinical and Research Blood): Participants will undergo repeat CBC with differential, serum chemistries, LFTs, coagulation studies and C-reactive protein within 5 days prior to planned surgery. Research blood will be drawn simultaneously with these standard pre-operative labs. NOTE: Participants will continue to take ruxolitinib until the morning of planned surgery. If surgery is delayed, participants will continue to take ruxolitinib and these pre-operative blood tests do not need to be repeated.
- Cross-sectional Imaging for Tumor Measurements (Research): Participants will undergo
 a repeat diagnostic CT scan of the neck with IV contrast within 5 days prior to planned
 surgery. If a neck MRI was performed in lieu of CT scan at baseline, then a MRI should
 be substituted at response assessment. NOTE: Participants will continue to take
 ruxolitinib until the morning of planned surgery. If surgery is delayed, participants will
 continue to take ruxolitinib and this pre-operative imaging does not need to be repeated.

NOTE: in the event that a patient lacks a CT-measurable primary tumor or metastatic lymph node, measurable disease may be established by caliper measurement of an oral cavity or oropharyngeal tumor (≥ 1 centimeter). In this case, caliper measurement should be repeated and documented within 5 days prior to planned surgery, as a substitute for cross-sectional imaging.

Phase 2 - Ruxolitinib Page 39 of 67

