7.1 Evaluation of Efficacy: Antitumor Effect – Solid Tumors

Response and progression in this study will be evaluated using the new international criteria proposed by the Response Evaluation Criteria in Solid Tumors (RECIST) Committee [JNCI 92(3):205-216, 2000]. Changes in only the largest diameter (unidimensional measurement) of the tumor lesions are used in the RECIST v1.1 criteria (or International Workshop on Chronic Lymphocytic Leukemia [IWCLL]).

7.1.1 **Definitions**

Evaluable for toxicity

All patients will be evaluable for toxicity from the time of their first treatment with the study drug.

Evaluable for objective response

Only those patients who have measurable disease present at baseline, have received at least one cycle of therapy, and have had their disease re-evaluated will be considered evaluable for response. These patients will have their response classified according to the definitions stated below. (Note: Patients who exhibit objective disease progression prior to the end of Cycle 1 will also be considered evaluable.)

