8.3 Interim Analyses and Stopping Rules

This is an open label biomarkers study. No interim analysis is planned.

8.4 **Analyses Plans**

8.4.1 **Analysis Populations**

Safety Population

The safety population will include all enrolled patients who receive at least one dose of ruxolitinib and have the potential to complete pharmacodynamics biomarkers assessments at baseline and the end of study treatment window. Although the risk from specimen collections for biomarker assessment is limited and low, all patients will be evaluable for toxicity and safety assessment of ruxolitinib. Patients who are determined ineligible after enrollment or who are not evaluable for safety analysis (e.g. due to withdrawal of consent or failure of specimens collection as not related to tumor progression and not treatment-related toxicity) will be replaced (see section 8.2.2 for details).

Efficacy Population

The efficacy population for the primary endpoint of 35% or greater reduction in tumor size will include all enrolled patients who have measurable disease present at baseline and have completed tumor assessment at the end of study window. Patients who are determined ineligible after enrollment or who are not evaluable for safety analysis (e.g. due to withdrawal of consent or failure of specimens collection as not related to tumor progression and not treatment-related toxicity) will be replaced (see section 8.2.2 for details).

Phase 2 - Ruxolitinib Page 50 of 67

Version date: 03-22-2023 Protocol CC# 16201

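### The evaluability rules disagree on patients who progress before day 14, and no section says which rule defines the set for the primary correlations

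*Combined protocol and SAP*

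**What the plan says.** - **Section 7.1.1** requires one cycle of therapy and a re-evaluation for objective response, then adds an exception: "Patients who exhibit objective disease progression prior to the end of Cycle 1 will also be considered evaluable". Cycle 1 is not defined there. Table 5.1 in section 5.1 gives the cycle length as "Pre-operative window (14-21 days) or up to 28 days for delayed" surgery.
- **Section 6.3.2.1**: "Fourteen days is the minimum required treatment for a patient to be considered evaluable". No exception is made for progression.
- **Section 3.5.1**, on patients who discontinue: one who had screening tissue, "has taken at least 14 days of drug, and has undergone response assessment, they are evaluable".
- **Section 3.4** lists "Progressive disease at any time" among the events that end treatment.
- **Section 2.3.1** defines the primary endpoint as change in tumor size "measured as a proportional percent (range -100% to +100%) from baseline to day 14-21".
- **Section 8.4.1** builds the efficacy population from measurable baseline disease and a tumor assessment at the end of the study window, with no minimum exposure. Its example of a replaceable loss is "failure of specimens collection as not related to tumor progression and not treatment-related toxicity".
- **Section 8.2.2** replaces patients who lack the tumor assessments and biomarker measurements at both time points. It makes no exception for progression and does not mention days on drug.
- **Section 8.4.2** specifies five Spearman correlations with percent change in tumor size and names no analysis set.

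**The concern.** A patient whose tumor is found to have progressed before day 14 stops drug with fewer than 14 days taken. Section 7.1.1 counts that patient as evaluable and section 6.3.2.1 does not. Under the second rule, the reason for leaving the set is a bad value of the primary outcome itself.

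Trimming the growth end of the outcome narrows its range. Real biomarker correlations are then estimated too close to zero, and power falls in a study that has only 23 patients for these tests. The secondary objective of preliminary efficacy (section 2.2) is also affected, because average change in tumor size looks better once the worst growers are gone. As the study is open label and the rule is unsettled, the choice of set could be made after the outcomes are known.

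**Working it through.** **Can the case arise?** Surgery falls on days 14 to 28 and the pre-surgical scan within 5 days before it, so the earliest scheduled scan is on day 14 − 5 = 9, which matches the heading of section 6.3.2.2. Scheduled detection before day 14 is therefore possible on days 9 to 13 only. Suppose two patients are scanned on day 10. The one without progression continues drug, reaches 14 days and is analysed, and section 6.3.2.2 does not ask for the scan to be repeated if surgery slips. The one with progression stops drug and fails the 14-day minimum.

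**The plan's own figure.** Section 8.2.1 gives an overall alpha of .15 over five hypotheses, so .15/5 = .03 each, and says 25 patients allow a two-tailed Spearman test to detect a correlation of .56. By Fisher's z at 80% power:

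n = ((z₀.₉₈₅ + z₀.₈₀)/atanh(.56))² + 3 = ((2.170 + 0.842)/0.633)² + 3 = 25.65, so 26 against the stated 25.

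Power at n = 25: Φ(0.633 × √22 − 2.170) = .788. At the planned n = 23: Φ(0.633 × √20 − 2.170) = .745. The stated figure reproduces to within one patient.

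**Effect of removing early progressors.** Simulation inputs:
- from section 8.2.1: correlation .56, n = 23, two-sided alpha .03;
- assumed: bivariate normal data, Spearman test by the t approximation, and removal of exactly the largest growers with refilling to 23.

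The removal shares are assumptions. With refilling, share c corresponds to an expected 23/(1 − c) − 23 patients removed.

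| Share removed | Patients removed | Mean Spearman | Power |
|---|---|---|---|
| 0% | 0 | .52 | .69 |
| 2% | 0.5 | .50 | .65 |
| 5% | 1.2 | .49 | .61 |
| 10% | 2.6 | .46 | .55 |
| 20% | 5.8 | .42 | .47 |

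Repeated runs agree to about .01. The first row has mean Spearman .52 rather than .56 because a Pearson correlation of .56 corresponds to a smaller rank correlation. Its power is below the .745 above because the Fisher formula ignores the lower efficiency of the rank statistic.

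**False positives.** With a true correlation of 0, the rejection rate stays at .029 to .033 for every share removed. Selection on tumor outcome alone creates no association with the biomarker. If exclusion also depended on the biomarker, the direction of bias would be open.

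**The case against.** A reader might infer that the plan requires early progressors to be dropped and replaced, so that the primary correlations are bound to be computed without the worst outcomes. The documents do not support that. The only section that defines an efficacy population, 8.4.1, has no 14-day condition, and its replacement example leaves out progression-related losses. Section 8.2.2 replaces for missing data, so an early progressor with a repeat scan and paired tissue would not be replaced under it. Section 3.5.1 says who is evaluable after discontinuing. It is a sufficient condition, not an exclusion, so only section 6.3.2.1 states a minimum.

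Three further points have weight:
- The main clause of 7.1.1 (one cycle of therapy) agrees with a 14-day minimum. Only its exception conflicts, and it may have been meant for RECIST classification rather than for the biomarker analysis. The documents do not say.
- The affected group may be nearly empty, given the narrow window for scheduled detection.
- Removing exactly the upper tail is a worst case. Sections 7.1.4 and 8.4.1 do not equate progression with the largest percent change: a new lesion also counts as progression, and such a patient need not be among the largest growers.

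Requiring 14 days of exposure is also defensible in a pharmacodynamic window study. What remains is that the text gives two answers for the same patient, does not say which governs the primary tests, and leaves replacement unsettled.

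**Conclusion.** The inconsistency is real and should be settled before analysis. Its consequence is conditional: only if the 14-day minimum defines the primary set are patients removed because of the outcome analysed. The harm is then attenuation, lost power and a flattering picture of tumor response. Inflated type I error is not shown.

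The size cannot be fixed from the documents. They give no early-progression rate, and the step from 45 enrolled to 23 evaluable is attributed to compliance and specimen quality. The lower rows of shares are the likelier ones: 2 to 5% removed takes power from about .69 to .65 or .61. The 20% row is an outer bound. The .56 is the plan's detectable value, and the prior correlations it cites concern Ki-67, not tumor size. The simulation assumes a continuous marker, so it does not describe the yes/no silencing marker of hypothesis 4.

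**What to change.** Change the analysis wording in sections 2.3.1, 6.3.2.1, 8.2.2 and 8.4.1, and in 3.5.1 for consistency:

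1. Name one primary efficacy set for the Spearman correlations. A patient with documented progression on ruxolitinib before day 14 stays in it, is assigned the worst rank for percent change in tumor size (tied if there are several), and is not replaced.
2. State in 2.3.1 that this outcome is accepted although it is determined before the day 14-21 window.
3. Include these patients for hypotheses 1, 4 and 5, which use baseline markers. For hypotheses 2 and 3, include them only when post-treatment tissue exists, and report how many are missing.
4. Report the set with at least 14 days of drug as a sensitivity analysis.

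The cost is a wording amendment. The downside is that a few patients contribute an outcome determined before day 14. Nothing here concerns when treatment is stopped.

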7.1.2 Disease Parameters

Measurable disease

Measurable disease is defined as lesions (or tumors) that can be accurately measured in at least one dimension (longest diameter to be recorded) with a minimum size of 10mm by CT scan (irrespective of scanner type) and MRI (no less than double the slice thickness and a minimum of 10mm), 10mm caliper measurement by clinical exam (when superficial), and/or 20mm by chest X-ray (if clearly defined and surrounded by aerated lung).

All tumor measurements will be recorded in millimeters or decimal fractions of centimeters. Previously irradiated lesions are considered non-measurable except in cases of documented progression of the lesion since the completion of radiation therapy.

Phase 2 - Ruxolitinib Page 41 of 67

Protocol CC# 16201

Target lesions

All measurable lesions up to a maximum of 5 lesions total (and a maximum of two lesions per organ) representative of all involved organs should be identified as target lesions and recorded and measured at baseline. Target lesions will be selected on the basis of their size (lesions with the longest diameter) and their suitability for accurate repeated measurements (either by imaging techniques or clinically). A sum of the longest diameter (LD) for all target lesions will be calculated and reported as the baseline sum LD. The baseline sum LD will be used as reference by which to characterize the objective tumor response.

Non-target lesions

All other lesions (or sites of disease) including any measurable lesions over and above the 5 target lesions should be identified as non-target lesions and should also be recorded at baseline. It is possible to record multiple non-target lesions involving the same organ as a single item on the case record form (e.g. "multiple enlarged pelvic lymph nodes" or "multiple liver metastases"). Bone lesions may be measureable if ≥ 1 cm on MRI. Measurements of these lesions are not required, but the presence or absence of each will be noted throughout follow-up.

Non-measurable disease (Tumor Markers)

Non-measurable disease is all other lesions (or sites of disease), including small lesions (longest diameter < 20 mm with conventional techniques or < 10 mm using spiral CT scan). Leptomeningeal disease, ascites, pleural or pericardial effusion, inflammatory breast disease, lymphangitic involvement of skin or lung, abdominal masses/abdominal organomegaly identified by physical exam that is not measurable by reproducible imaging techniques are all non-measurable. (e.g., PSA, CA-125, CA19-9, CEA)

7.1.3 Methods for Evaluation of Measurable Disease

All measurements will be taken and recorded in metric notation using a ruler or calipers. All baseline evaluations will be performed as closely as possible to the beginning of treatment and never more than 28 days before the beginning of the treatment.

The same method of assessment and the same technique will be used to characterize each identified and reported lesion at baseline and during follow-up. Imaging-based evaluation is preferred to evaluation by clinical examination when both methods have been used to assess the antitumor effect of a treatment.

7.1.4 Response Criteria

Complete Response (CR)

Disappearance of all target lesions, determined by two separate observations conducted not less than 4 weeks apart. Any pathological lymph nodes (whether target or non-target) must have reduction in short axis to <10 mm (the sum may not be "0" if there are target nodes). There can be no appearance of new lesions.

Phase 2 - Ruxolitinib Page 42 of 67

Protocol CC# 16201

Partial Response (PR)

At least a 30% decrease in the sum of the longest diameter (LD) of target lesions, taking as reference the baseline sum LD. There can be no appearance of new lesions.

Progressive Disease (PD)

At least a 20% increase in the sum of the SLD of target lesions, taking as reference the smallest sum SLD recorded since the treatment started and minimum 5 mm increase over the nadir, or the appearance of one or more new lesions.

Stable Disease (SD)

Neither sufficient shrinkage to qualify for PR nor sufficient increase to qualify for PD, taking as reference the smallest sum LD since the treatment started.

Evaluation of Non-Target Lesions

Complete Response (CR)

Disappearance of all non-target lesions and normalization of tumor marker level. All lymph nodes must be non-pathological in size (< 10 mm short axis).

Incomplete Response/Stable Disease (SD)

Persistence of one or more non-target lesion(s) and/or maintenance of tumor marker level above the normal limits.

Progressive Disease (PD)

Appearance of one or more new lesions and/or unequivocal progression of existing non-target lesions.

Evaluation of Best Overall Response

The best overall response is the best response recorded from the start of the treatment until disease progression.

Evaluation of Target Lesions

Complete Response (CR)

Disappearance of all target lesions. Any pathological lymph nodes (whether target or non-target) must have reduction in short axis to <10 mm.

Partial Response (PR)

At least a 30% decrease in the sum of target lesion diameters (longest diameter of non-nodal lesions; short axis diameter of the target lymph nodes), /recurrence (taking as reference the baseline sum diameter.

Progressive Disease (PD)

At least a 20% increase in the sum of target lesion diameters (longest diameter of non-nodal lesions; short axis diameter of the target lymph nodes), taking as reference for progressive disease the smallest *sum diameter* measurements recorded since the baseline sum diameter measurements. In addition to the relative increase of 20%, the sum must also demonstrate an absolute increase of at least 5 mm. Note: the appearance of one or more new lesions is also considered progressions. The patient's best response assignment will depend on the achievement of both measurement and confirmation criteria.

Phase 2 - Ruxolitinib Page 43 of 67

Protocol CC# 16201

Table 2.1 Response Criteria

Target Lesions	Non-Target Lesions	New Lesions	Overall Response	Best Response for this Category Also Requires	
CR	CR	No	CR	> 4 weeks confirmation	
CR	Non-CR/ Non-PD	No	PR	> 4 weeks confirmation	
PR	Non-PD	No	PR		
SD	Non-PD	No	SD	documented at least once > 4 weeks from baseline	
PD	Any	Yes or No	PD		
Any	PD*	Yes or No	PD	no prior SD, PR or CR	
Any	Any	Yes	PD		

^{*} In exceptional circumstances, unequivocal progression in non-target lesions may be accepted as disease progression

Progression-Free Survival

Progression-free survival (PFS) is defined as the duration of time from start of treatment to time of progression.

